7.5.4. Management of Bone Evaluation

As there is uncertainty surrounding the clinical significance and management of decreases in bone mineral density for chronic HBV-infected patients, Gilead recommends that any subject who has a DXA scan that demonstrates a decrease from baseline of > 5% in bone mineral density of the spine region or the hip region be followed per local medical practice at the discretion of the investigator.

7.5.5. On-Treatment ALT Flare and Post-Treatment Exacerbation of Hepatitis Management

On-Treatment ALT Flare is defined as:

• Confirmed (within 3 days of receipt of initial laboratory results) serum ALT > $2 \times$ baseline value and > $10 \times$ ULN, with or without associated symptoms

7.5.5.1. Management of ALT Flare in Subjects Receiving Study Medication

If laboratory results indicate elevation of ALT $> 2 \times$ baseline and $> 10 \times$ ULN, the following is recommended:

- Schedule the subject to return to the clinic as soon as possible (ideally within 3 days after initial laboratory results were drawn). During the visit, a clinical assessment of the subject will be performed. The assessment should include a physical examination and evaluation of the subject's mental status.
- Check the following laboratory parameters: serum ALT and AST, total bilirubin, INR, and serum albumin.
- If the ALT elevation is confirmed, the central clinical laboratory will conduct reflex testing for plasma HBV DNA, serology for HBV (HBsAg and HBsAb), HDV, HAV IgM, HCV, and HEV.

Based on the results of the confirmatory tests, the following treatment modifications are recommended:

Elevated Liver Enzymes, Normal or Stable relative to baseline Liver Function Tests

If ALT levels are elevated (i.e., $> 2 \times$ baseline and $> 10 \times$ ULN) with normal or stable total bilirubin and INR relative to baseline, the subject may remain on study medication and should be monitored weekly as long as ALT levels return to normal or baseline level.

During monitoring, if the ALT values remain persistently elevated, the investigator should discuss with the Gilead Medical Monitor whether the study drug should be discontinued.

For subjects with bridging fibrosis or cirrhosis, study drug discontinuation with treatment-free follow-up is to be avoided due to the potential risk of exacerbation of hepatitis in the setting of low hepatic reserve which could lead to decompensation. Subjects with bridging fibrosis or cirrhosis should be placed on commercially available HBV therapy following study drug discontinuation.

Elevated Liver Enzymes, Elevated Liver Function Tests

If ALT values are elevated (i.e., $> 2 \times$ baseline and $> 10 \times$ ULN), and total bilirubin is confirmed to be $2 \times$ baseline value, and INR is 0.5 above baseline, provided both are > ULN, the investigator should consider discontinuing study medication (upon discussion with the Gilead Medical Monitor, unless the safety of the subject is of immediate concern).

The subject should be monitored weekly as long as ALT, total bilirubin, and INR values remain elevated or above baseline values.

During monitoring, if the ALT values and the liver function tests remain persistently elevated, the investigator should discuss with the Gilead Medical Monitor whether the study drug should be discontinued.

For subjects with bridging fibrosis or cirrhosis, study drug discontinuation with treatment-free follow-up is to be avoided due to the potential risk of exacerbation of hepatitis in the setting of low hepatic reserve which could lead to decompensation. Subjects with bridging fibrosis or cirrhosis should be placed on commercially available HBV therapy following study drug discontinuation.

7.5.5.2. Management of Exacerbation of Hepatitis in Subjects Who Have Discontinued Study Medication

If laboratory results indicate (1) an ALT elevation $> 2 \times$ baseline and $> 10 \times$ ULN alone OR associated with (2) abnormal laboratory parameters suggestive of worsening hepatic function (total bilirubin 2 \times baseline, INR 0.5 above baseline, provided both are > ULN) and the subject is on no post-study therapy for HBV, the following is recommended:

- Schedule the subject to return to the clinic as soon as possible (ideally no later than 3 days after the initial laboratory values were drawn). During the visit, perform a clinical assessment of the subject.
- Check the following laboratory parameters: serum ALT and AST, total bilirubin, INR, and albumin.
- If the ALT elevation is confirmed, the central clinical laboratory will conduct reflex testing for plasma HBV DNA, serology for HBV (HBsAg and HBsAb), HDV, HAV IgM, HCV and HEV. If Plasma HBV DNA is increasing, the investigator should consider immediate initiation of approved therapy.
- The subject should be followed until laboratory parameters (ALT, total bilirubin, INR) return to normal or baseline up to a maximum of 6 months after the initial occurrence of the event.

7.5.7. Management of Potential Nephrotoxicity

Creatinine clearance (CL_{Cr}), estimated according to the Cockcroft-Gault formula, will be followed post-baseline during the study. All subjects with estimated $CL_{Cr} < 50$ mL/min must have serum creatinine measured again within 3 calendar days of receipt of results. At the time of this repeat serum creatinine assessment, serum Cystatin C will also be measured and the estimated glomerular filtration rate (eGFR) by CKD-EPI (cystatin C) will be calculated and compared with the baseline measurement of this parameter. During the double-blind period, any subject who has a confirmed CL_{Cr} estimated by the Cockroft-Gault formula < 50 mL/min and also experiences a > 20% reduction in eGFR by CKD-EPI (cystatin C) from baseline, will be managed as described below:

CKD-EPI (cystatin C) formula adjusted for age and sex:

eGFR (mL/min/1.73m²) =
$$133 \times \min(\text{Scys/0.8}, 1)^{-0.499} \times \max(\text{Scys/0.8}, 1)^{-1.328} \times 0.996^{\text{Age}} \times 0.932 \text{ if female}$$

where Scys is serum cystatin C (mg/L), min (Scys/0.8,1) indicates the minimum of Scys/0.8 or 1, and max (Scys/0.8,1) indicates the maximum of Scys/0.8 or 1.

During the double-blind period, subjects meeting the above eGFR criteria (i.e. confirmed CL_{Cr} < 50 mL/min by Cockcroft-Gault equation and > 20% reduction from baseline in eGFR by CKD-EPI equation) will be managed as follows:

- If the CL_{Cr} is confirmed to be ≥ 30 mL/min and < 50 mL/min, the subject will be required to undergo dose modification to every other day dosing of study drug.
- If the CL_{Cr} is confirmed ≥ 30 mL/min to < 50 mL/min and the subject has undergone dose modification to every other day dosing of study drug and subsequently develops a confirmed $CL_{Cr} \geq 50$ mL/min, the subject may revert to once daily dosing of study drug after discussion with the Gilead Medical Monitor.
- If the CL_{Cr} is confirmed to be < 30 mL/min, the subject will be required to permanently discontinue study drug.

During the open-label TAF 25 mg extension period, subjects who meet the above eGFR criteria (i.e. confirmed $CL_{Cr} \geq 30$ mL/min to < 50 mL/min and > 20% reduction from baseline in eGFR by CKD-EPI equation) are not required to undergo dose modification to every other day dosing of study drug, and subjects with confirmed $CL_{Cr} < 30$ mL/min are not required to permanently discontinue study drug.

All subjects with negative or trace proteinuria at baseline that develop $\geq 1+$ proteinuria on urinalysis are recommended to have a urinalysis repeated, with a concurrent urinalysis and urine chemistry, within two weeks of receipt of results. Upon confirmation of new proteinuria, subjects will be asked to return to the clinic for a scheduled or unscheduled follow up visit for evaluation. It is recommended that the Investigator contact the Gilead Medical Monitor to discuss if further consultation with a nephrologist is clinically warranted.

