- Treatment Arm B: approximately 230 subjects administered Gilead-provided TDF 300 mg QD and matched placebo of TAF 25 mg QD

The duration of double blind treatment is 48 weeks. All subjects who complete 48 weeks of treatment are eligible for participation in the open label TAF 25 mg extension period for an additional 48 weeks (through Week 96). During the double-blind period only, subjects with a confirmed creatinine clearance by Cockcroft Gault Method (eGFR_{CG}) < 50 ml/min, and > 20% decline in estimated glomerular filtration rate (eGFR_{CysC}) by CKD-EPI (cystatin C) compared to baseline during the study, will be required to undergo dose modification to every other day dosing of study drug. Subjects with confirmed creatinine clearance < 30 mL/min during the double-blind period of the study will have the study drug discontinued.

Subjects who permanently discontinue study drug (either prematurely or at the end of study [Week 96]) for reasons other than HBsAg loss with confirmed seroconversion to anti-HBs will be followed every 4 weeks for 24 weeks off treatment or until initiation of appropriate alternative, HBV therapy, whichever occurs first. Use of appropriate, alternative HBV therapy is strongly encouraged.

Subjects with HBsAg loss with confirmed seroconversion to anti-HBs should discontinue study drug within 3-6 months following confirmation of seroconversion to anti-HBs. Subjects with HBsAg loss with confirmed seroconversion prior to Week 48 are not permitted to discontinue study drug prior to the Week 48 visit. Subjects with HBsAg loss with confirmed seroconversion will be followed off treatment every 4 weeks for 12 weeks and then per the study visit schedule (Appendix 2) through Week 96/ED.

Discontinuation of study drug for subjects experiencing HBsAg loss with confirmed seroconversion, who have known bridging fibrosis or cirrhosis, should be considered on a case by case basis.

The primary analysis will occur at Week 48 with the primary efficacy endpoint being the proportion of subjects with HBV DNA ≥ 20 IU/mL, as determined by the modified US FDA-defined snapshot algorithm.

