Key secondary safety endpoints include the percent change from baseline at Week 48 in hip and spine BMD, and the change from baseline at Week 48 in eGFR_{CG}. During the double-blind period of the study if a subject has a confirmed creatinine clearance (eGFR_{CG}) < 50 ml/min with a > 20% decline from baseline in eGFR by CKD-EPI_{CysC}, the subject will be required to undergo dose modification to every other day dosing of study drug. During the double-blind period, subjects with confirmed eGFR_{CG} < 30 mL/min will have the study drug discontinued.

The proportion of subjects in each treatment arm with tolerability failure (defined as an adverse event [AE] leading to permanent discontinuation of study drug) at Week 48 will be summarized. Percent change from baseline in BMD by DXA of the hip and spine hip will be assessed at Weeks48 and 96. Change from eGFR_{CG} will be assessed at every visit and summarized through Week 48. Adverse events and clinical laboratory tests will be collected at every visit and summarized through Week 48. Additionally, summaries of AEs, discontinuations due to AEs, and laboratory data including BMD measurements (via DXA scans and eGFR_{CG}) by original treatment arms (TAF versus TDF) will continue on an annual basis through Week 96.

Efficacy:

The primary efficacy endpoint is:

 Proportion of subjects with HBV DNA ≥ 20 IU/mL (as determined by the modified US FDA-defined snapshot algorithm) at Week 48

The secondary efficacy endpoints are:

- Proportion of subjects with HBV DNA ≥ 20 IU/mL (as determined by the modified US FDA-defined snapshot algorithm) at Week 96
- Proportion of subjects with serological response (loss of Hepatitis B s antigen [HBsAg] and seroconversion to anti-HBs, and loss of Hepatitis B e antigen [HBeAg] and seroconversion to anti-HBe in HBeAg-positive subjects) at Weeks 48 and 96
- Proportion of subjects with biochemical response (normal ALT and normalized ALT) at Weeks 48 and 96
- Change from baseline in fibrosis as assessed by FibroTest® at Weeks 48 and 96
- Proportion of subjects with HBV DNA < 20 IU/mL and target detected/not detected (i.e. < LLOD) at Weeks 48 and 96

Statistical Methods:

The primary analysis will be performed when the last subject has completed Week 48 assessments or discontinued prematurely. The analysis will compare the TAF arm to the TDF arm.

Analysis Methods:

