3. STUDY DESIGN

3.1. Study Treatment Plan and Regimen

This is a randomized, double-blind, multicenter, active-controlled study to evaluate the safety and efficacy of TAF 25 mg QD in virologically suppressed subjects who switch from TDF to TAF compared to continued TDF treatment.

Approximately 460 subjects (with approximately 50% of subjects being \geq 50 years old) will be randomized in a 1:1 ratio (A:B) to receive either TAF 25 mg QD and matched placebo of TDF 300 mg QD or Gilead-provided TDF 300 mg QD and matched placebo of TAF 25 mg QD.

At randomization, subjects will be stratified by screening HBeAg status (HBeAg-negative vs. HBeAg-positive) and age (> 50 or < 50 years).

- Treatment Arm A: approximately 230 subjects administered TAF 25 mg QD and matched placebo of Tenofovir DF (TDF) 300 mg QD
- Treatment Arm B: approximately 230 subjects administered Gilead-provided TDF 300 mg QD and matched placebo of TAF 25 mg QD

The duration of double blind treatment is 48 weeks. All subjects who complete 48 weeks of treatment are eligible for participation in the open label TAF 25 mg extension period for an additional 48 weeks (through Week 96). During the double-blind period, subjects with a confirmed creatinine clearance by Cockcroft Gault Method (eGFR_{CG}) < 50 ml/min, and > 20% decline in eGFR by CKD-EPI (cystatin C) compared to baseline during the study, will be required to undergo dose modification to every other day dosing of study drug. Subjects with confirmed creatinine clearance < 30 mL/min during the double blind phase of the study will have the study drug permanently discontinued. Subjects with confirmed eGFR_{CG} < 50 mL/min will not undergo dose modification to every other day during the open-label TAF 25 mg extension period, nor will treatment be permanently discontinued for confirmed eGFR_{CG} < 30 mL/min during the open-label extension period.

Subjects who permanently discontinue study drug (either prematurely or at the end of study [Week 96]) for reasons other than HBsAg loss with confirmed seroconversion to anti-HBs will be followed every 4 weeks for 24 weeks off treatment or until initiation of appropriate alternative, HBV therapy, whichever occurs first. Use of appropriate, alternative HBV therapy is strongly encouraged.

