6.6. Criteria for Discontinuation of Study Treatment

Study medication may be discontinued in the following instances:

- Intercurrent illness that would, in the judgment of the investigator, affect assessments of clinical status to a significant degree. Following resolution of intercurrent illness, the subject may resume study dosing at the discretion of the investigator.
- Unacceptable toxicity, or toxicity that, in the judgment of the investigator, compromises the ability to continue study-specific procedures or is considered to not be in the subject's best interest
- Subjects with confirmed creatinine clearance of < 30 mL/min during the double blind phase of the study will have their study drug permanently discontinued
- HBsAg loss with seroconversion to anti-HBs. These subjects should discontinue study drug
 within 3-6 months following confirmation of seroconversion to anti-HBs. Subjects with
 HBsAg loss with confirmed seroconversion before Week 48 are not permitted to discontinue
 study drug prior to the Week 48 visit
- Discontinuation of study drug for subjects experiencing HBsAg-loss with confirmed seroconversion to anti-HBs, who have known bridging fibrosis or cirrhosis, should be considered on a case by case basis
- Therapeutic failure
- Subject request to discontinue for any reason
- Subject noncompliance
- Pregnancy during the study; refer to Appendix 5
- Discontinuation of the study at the request of Gilead, a regulatory agency or an institutional review board or independent ethics committee (IRB/IEC)

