1.2.4. Study Periods and Phases

The duration of double-blind treatment is 48 weeks. All subjects who complete 48 weeks of treatment are eligible for participation in the open label TAF 25-mg extension period for an additional 48 weeks (through Week 96). During the double-blind period only, subjects with a confirmed eGFR $_{CG}$ < 50 ml/min, and > 20% decline in estimated glomerular filtration rate (eGFR $_{CysC}$) by CKD-EPI (cystatin C) compared to baseline during the study, were required to undergo dose modification to every other day dosing of study drug. Subjects with confirmed creatinine clearance < 30 mL/min during the double-blind period of the study were to have the study drug discontinued.

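### Section 7.5.7 makes the double-blind stop at confirmed CLcr < 30 mL/min depend on a > 20% cystatin C decline; four other protocol statements and the SAP make it unconditional

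*Protocol*

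**What the plan says.** Protocol Section 7.5.7 requires a repeat serum creatinine and a cystatin C measurement for any CLcr below 50 mL/min. It then sets a joint condition for double-blind dose actions: confirmed CLcr < 50 mL/min and a reduction of more than 20% from baseline in cystatin C eGFR. The condition is stated once in the opening paragraph and again in the lead-in to the bullets, which begins "During the double-blind period, subjects meeting the above eGFR criteria". Three bullets follow:

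- every-other-day dosing at CLcr 30 to < 50;
- a route back to daily dosing on recovery;
- at confirmed CLcr < 30, "the subject will be required to permanently discontinue study drug".

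The closing open-label sentence is built differently. It attaches the cystatin C criterion to the 30 to < 50 band only, and says separately that subjects with confirmed CLcr < 30 "are not required to permanently discontinue study drug".

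The double-blind stop appears in five other places, each time without a cystatin C condition:

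- Protocol Synopsis, Study Design: "Subjects with confirmed creatinine clearance < 30 mL/min during the double-blind period of the study will have the study drug discontinued".
- Protocol Synopsis, Criteria for Evaluation (Safety), for confirmed eGFR by Cockcroft-Gault: "< 30 mL/min will have the study drug discontinued".
- Protocol Section 3.1: these subjects "will have the study drug permanently discontinued".
- Protocol Section 6.6: these subjects "will have their study drug permanently discontinued".
- SAP Section 1.2.4: subjects below 30 mL/min "during the double-blind period of the study were to have the study drug discontinued".

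**The concern.** Take a double-blind subject whose confirmed CLcr is 28 mL/min and whose cystatin C eGFR has fallen 15%. The five statements above stop the drug. Section 7.5.7 lists neither a stop nor a dose change, because the subject fails its joint condition. It does not order continuation; it is silent on dosing.

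Section 7.5.7 is headed as the management of potential nephrotoxicity, and it also tells the site to measure cystatin C at confirmation. A site applying its condition literally would miss a mandatory stop. Section 1.1 of the protocol acknowledges that the control drug is associated with nephrotoxicity in some subjects. By inference, the same wording could delay a stop while a cystatin C result is pending, or block it if the baseline value is missing.

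**Working it through.** **Step 1. Compare the rules.** Apply 7.5.7 alone, and then the other five statements together, to the same double-blind subjects.

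| Confirmed CLcr (mL/min) | Cystatin C eGFR fall | 7.5.7 read alone | Other five statements |
|---|---|---|---|
| 55 | 10, 20, 21 or 30% | no dose action | no dose action |
| 40 | 10 or 20% | no dose action | no dose action |
| 40 | 21 or 30% | every other day | every other day |
| 29 | 10 or 20% | **no dose action** | **stop** |
| 29 | 21 or 30% | stop | stop |

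They differ only where CLcr is < 30 and the decline is 20% or less. Moving the < 30 bullet out of the cystatin C condition makes every row agree.

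**Step 2. How far CLcr must fall.** Entry requires CLcr ≥ 50 (Section 4.2). At fixed age and weight, Cockcroft-Gault is inversely proportional to serum creatinine.

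- From 50 to 30: fall = 1 − 30/50 = 40%; creatinine ratio = 50/30 = 1.67.
- From 60 to 30: fall = 1 − 30/60 = 50%; creatinine ratio = 60/30 = 2.0.

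Getting below 30 needs more than these.

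**Step 3. How far cystatin C may rise.** The 7.5.7 formula has exponent −1.328 when cystatin C is at or above 0.8 mg/L and −0.499 when it is at or below 0.8 mg/L. Ignoring the small age change, the ratio that gives exactly a 20% fall is:

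- at or above 0.8 mg/L at both times: 0.8^(−1/1.328) = 1.183, a rise of 18.3%;
- at or below 0.8 mg/L at both times: 0.8^(−1/0.499) = 1.564, a rise of 56.4%.

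Up to those rises the subject stays outside the 7.5.7 condition.

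**Step 4. A worked subject (assumed values).** Man, 65 years, 60 kg.

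- Creatinine 1.14 mg/dL: CLcr = (140 − 65) × 60 / (72 × 1.14) = 54.8 mL/min.
- Creatinine 2.23 mg/dL: CLcr = 4500 / (72 × 2.23) = 28.0 mL/min.
- Cystatin C 1.00 mg/L: eGFR = 133 × (1.00/0.8)^(−1.328) × 0.996^65 = 76.2.
- Cystatin C 1.13 mg/L: eGFR = 133 × (1.13/0.8)^(−1.328) × 0.996^65 = 64.8.
- Fall = 1 − 64.8/76.2 = 15.0%.

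The five statements stop him; 7.5.7 lists no dose action.

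**Step 5. Do the grade-based rules in Section 7.5 catch him?** Appendix 4 makes creatinine Grade 2 from > 2.00 to 3.00 mg/dL and Grade 3 only above 3.00. He crosses CLcr 30 at 4500 / (72 × 30) = 2.08 mg/dL, and Grade 3 begins only beyond CLcr 4500 / (72 × 3.00) = 20.8 mL/min. At 2.23 mg/dL he is Grade 2, and Section 7.5.1 leaves continuation to the investigator.

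**The case against.** The strongest reply is that the protocol already gives the instruction. Section 6.6 is the section on stopping study drug and states the rule without a cystatin C condition, as do Section 3.1 and the synopsis. Silence in one section plus an express rule elsewhere is not a contradiction, and Section 9.1.9 binds investigators to the whole protocol. The open-label sentence in 7.5.7 confirms the intent. On this view the fault is editorial: no threshold, test or strategy is in dispute.

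Much of this stands. A site that reads the whole protocol would stop the drug. Only a dose action is missing from 7.5.7, since repeat testing is still required. The SAP statement describes the design and does not instruct sites, so four statements do that. Appendix 3, to which Section 7.5 refers, is not in the supplied text and cannot be relied on either way.

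The event is also rare. In the two Phase 3 hepatitis B studies, confirmed renal laboratory abnormalities of any listed kind occurred in 0.6% on TAF and 1.6% on TDF (Section 1.2.3). If those rates carried over to this different, virologically suppressed population, they would give 230 × 0.006 = 1.4 and 230 × 0.016 = 3.7 subjects per arm. The disputed case would be a small part of that.

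Finally, SAP Section 2.2 reports the Week 48 analysis as done, so rewording would no longer protect double-blind subjects.

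None of this removes the fault. A safety stop is conditional in the section devoted to kidney toxicity and unconditional elsewhere. Step 5 shows that the grading rules do not close the gap, and the list in Section 6.6 opens in permissive terms even though its renal bullet is mandatory.

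**Conclusion.** The concern holds. Section 7.5.7 as written attaches a cystatin C condition to a stop that four other protocol statements and the SAP make unconditional. The condition belongs only to every-other-day dosing, so the < 30 bullet is misplaced.

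The practical size is small: an expected count near zero if the Phase 3 renal rates transfer. Sample size, power and alpha do not change. The primary endpoint numerator is essentially unaffected, because a stopped subject whose last on-treatment HBV DNA was < 20 IU/mL, with no on-treatment Week 48 value, is classed as having no virologic data (Section 8.6.1.1).

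The conclusion about the text needs no numerical assumption. The figures in Steps 2 and 3 assume constant age and weight, and the Step 4 subject is hypothetical. The correction should be made because it concerns subject safety and involves no scientific trade-off; the fault does not threaten the trial.

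**What to change.** Take the third bullet of Section 7.5.7 out of the joint condition and state it separately, for example: *In the double-blind period, confirmed CLcr < 30 mL/min requires permanent discontinuation of study drug, whatever the change in cystatin C eGFR.* Keep the > 20% cystatin C condition for every-other-day dosing at CLcr 30 to < 50 mL/min. The cost is one bullet and a note to sites, with no change to data collection, the SAP or the sample size.

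Since the double-blind period appears to be over, list every double-blind subject with confirmed CLcr < 30 mL/min, check that study drug was permanently stopped, and report any who continued. Correct the wording before the section is reused in another protocol.
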